3.1.1 Dose-Limiting Toxicity

DLTs will be assessed during the safety run-in portion of the study. Patients will be replaced for DLT evaluation if they do not complete the DLT evaluation period and do not experience a DLT before they discontinue from the study or start subsequent cancer therapy.

The DLT evaluation period for each safety run-in patient is defined as 28 days after the first dose of tisotumab vedotin. Patients who experience DLTs should not receive further treatment with tisotumab vedotin, unless clinical benefit is demonstrated with adequately managed toxicity. Subsequent treatment with tisotumab vedotin will be defined by the medical monitor in discussion with the site investigator in the context of the type of AE observed.

The IB for tisotumab vedotin describes AEs commonly observed, as well as less common serious findings. The IB should be referenced when attributing causality; however, the final decision regarding causality is at the discretion of the investigator.

A DLT is defined as:

One of the following that is observed within **28 days** of the first dose of tisotumab vedotin and is considered related to the drug:

- Grade 4 neutropenia (i.e., ANC $<0.5 \cdot 10^9$ cells/L) for minimal duration of seven days.
- Grade 3 and 4 febrile neutropenia (i.e., ANC $<1.0 \cdot 10^9$ cells/L with a single temperature of $>38.3^{\circ}\text{C}$ or a sustained temperature of $\geq 38^{\circ}\text{C}$ for more than one hour).
- Grade 4 thrombocytopenia ($\leq 25.0 \cdot 10^9$ platelets/L).
- Grade 3 thrombocytopenia associated with bleeding episodes.
- Grade 3 or higher ocular adverse events
- Major bleeding, defined as:
 - Fatal bleeding
 - Symptomatic bleeding in a critical area organ, such as intracranial, intraocular, retroperitoneal, intra-articular or pericardial, or intramuscular with compartment syndrome
 - Bleeding causing a drop in hemoglobin level of 20 g/L (1.24 mmol/L) or more
 - Bleeding leading to transfusion of two or more units of whole blood or red cells.
- Stevens Johnson syndrome, toxic epidermal necrolysis, Grade ≥ 3 cutaneous vasculitis.
- Grade 3 neuropathy (not improving to Grade 1 within 3 weeks following end of treatment) and Grade 4 neuropathy.
- Grade 3 infusion -related AEs that do not resolve to Grade 1 or baseline within 24 hours.
- Grade 4 infusion -related events including anaphylaxis.
- Any Grade ≥ 3 non-hematological AEs which occur during the first treatment cycle and are at least possibly study drug related, excluding non-hematological laboratory abnormalities that have no clinical consequences and resolve within 48 hours.
- Grade ≥ 3 diarrhea and/or vomiting persisting for more than 48 hours with optimal medical management.
- Grade ≥ 3 nausea (not disease-related) lasting 3 days or more with optimal medical management.

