Patients must have measurable disease at baseline according to RECIST v1.1. An Eastern Cooperative Oncology Group (ECOG) performance status of 0 or 1 and adequate cardiovascular, central nervous system (CNS), renal, and hematological function (including coagulation parameters) are required at baseline. Patients may not have active bleeding conditions, uncontrolled pleural/pericardial effusions, uncontrolled tumor-related pain, peripheral neuropathy \geq Grade 2, or ocular surface disease at the time of enrollment. Tumor TF expression will not be evaluated at screening or required for enrollment.

Number of Planned Patients

Approximately 222 patients may be enrolled in the study. This includes approximately 12 patients in the safety run-in phase as well as approximately 30 patients in each of 2 Part A cohorts with a possible expansion of up to approximately 70 additional patients in one of the 2 Part A cohorts. Part B will enroll approximately 80 patients including approximately 60 patients who have received 1 to 3 prior lines of therapy, including bevacizumab treatment.

Study Design

This is an open-label, phase 2 study with an initial safety run-in period. The safety run-in period will evaluate the safety of a dose-dense schedule and will start at a 0.9 mg/kg dose level. If 0.9 mg/kg is considered safe and tolerable, the dose level will be escalated to 1.2 mg/kg. Otherwise it will be de-escalated to 0.65 mg/kg. Each dose level will enroll approximately 6 patients. Patients who do not complete the DLT period will be replaced. A dose level is considered safe and tolerable if no more than 1 patient experiences a DLT among 6 patients during the DLT period. The highest dose level that is considered safe will be the recommended phase 2 dose (RP2D) and will be used in Part A. If no RP2D for the dose-dense schedule is identified, Part A will be a single arm of the Q3W regimen and Part B will not enroll.

In Part A, 60 patients will be randomized in a 1:1 ratio to receive tisotumab vedotin 2.0 mg/kg intravenously (IV) every 3 weeks (Q3W regimen) or the safety run-in RP2D on Days 1, 8, and 15 of every 4-week cycle (dose-dense regimen; 3Q4W) if a RP2D has been identified. Randomization will be stratified by first line vs. second line PROC and histology (serous vs. non-serous).

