Dose intensity of the 0.9 mg/kg dose-dense and 2.0 mg/kg Q3W regimens is similar, allowing exploration of whether a dose-dense schedule, with its different exposure profile, provides improved efficacy in ovarian cancer patients at the same dose intensity. Over a given cycle, the Q3W dose regimen at 2.0 mg/kg results in a dose intensity of 0.67 mg/kg/week, while the dose-dense regimen at 0.9 mg/kg 3 times every 4 weeks results in a dose intensity of 0.68 mg/kg/week. If DLTs are experienced in 2 or more patients at the 0.9 mg/kg dose during the safety run-in, a de-escalation of 28% to 0.65 mg/kg 3 times every 4 weeks will be explored. The 0.65 mg/kg dose level results in a dose intensity similar to a 1.5 mg/kg Q3W dose. In the GEN701 trial, at the 1.5 mg/kg Q3W dose, no DLTs were observed. Additionally, during dose escalation in the GEN701 trial, the 1.2 mg/kg Q3W dose was the lowest dose at which a partial response was observed, suggesting that 0.65 mg/kg 3 times every 4 weeks may be in the therapeutic range.

The full implementation of a comprehensive ocular mitigation strategy allows the re-exploration of the 1.2 mg/kg dose-dense regimen, if 0.9 mg/kg is deemed to be safe by the SMC. The 1.2 mg/kg dose-dense regimen represents an increase in dose intensity (33%) over the 0.9 mg/kg dose-dense regimen. The dose-dense regimens have lower maximum ADC plasma concentrations (C_{max}) and higher ADC trough plasma concentrations (C_{min}) compared to the 2.0 mg/kg Q3W dose regimen. These differences in pharmacokinetic profiles allow the further investigation of exposure-response relationships for optimal efficacy and safety.

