5.2.3 Dose Modifications

For patients who do not tolerate the protocol-specified dosing schedule, dose reductions are permitted in order to allow the patient to continue tisotumab vedotin treatment. Dose reductions must be preapproved by the sponsor's medical monitor unless allowed according to the mitigation plans specified in the protocol (please refer to Section 5.3). Once a dose is reduced, it should not be re-escalated for that patient during the study.

- If toxicities occur on Day 1 of any cycle and require the tisotumab vedotin dose to be held, then the start of the cycle may be delayed.
- If toxicities occur on Day 8 and require the dose to be held for >2 days, then the dose should be eliminated.
- If toxicities occur on Day 15 of any cycle and require the dose to be held >7 days, then the dose(s) should be eliminated.
- If a patient only receives tisotumab vedotin on Day 1 and needs to skip Days 8 and 15, the patient could resume the next cycle as early as Day 22 (new Day 1) per the mitigation plans specified in Section 5.3.

In case any dose reduction of tisotumab vedotin is needed, the dose must be reduced according to the guidelines provided below (Table 3 and Table 4)

Table 3: Dose modification scheme: Dose-dense regimen

Previous dose of tisotumab vedotin	Reduced dose of tisotumab vedotin
1.2 mg/kg (120 mg maximum total dose) on D1, D8, and D15	0.9 mg/kg (90 mg maximum total dose) on D1, D8, and D15
0.9 mg/kg (90 mg maximum total dose) on D1, D8, and D15	0.65 mg/kg (65 mg maximum total dose) on D1, D8, and D15
0.65 mg/kg (65 mg maximum total dose) on D1, D8, and D15	0.65* mg/kg (65 mg maximum total dose) on D1 and D8

* If the patient is already being treated with tisotumab vedotin 0.65 mg/kg on D1 and D8, the dose must not be reduced further.

Table 4: Dose modification scheme: Q3W regimen

Previous dose of tisotumab vedotin	Reduced dose of tisotumab vedotin
2.0 mg/kg (200 mg maximum total dose)	1.3 mg/kg (130 mg maximum total dose)
1.3 mg/kg (130 mg maximum total dose)	0.9* mg/kg (90 mg maximum total dose)

* If the patient is already being treated with tisotumab vedotin 0.9 mg/kg, the dose must not be reduced further.

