6.4 Treatment Period (Dose-Dense Regimen only)

6.4.1 Day 1 (± 1 day), All Treatment Cycles (Exceptions Noted)

- Cycle 1 only: Prior to dosing, confirm patient eligibility per inclusion/exclusion criteria
- Weight
- Physical Exam
- Predose vital signs
- ECOG Performance status (If Baseline Visit activities occur within 1 day prior, this assessment does not need to be repeated at Cycle 1, Day 1)
- Chemistry panel (results to be submitted to central laboratory; if Baseline Visit activities occur within 1 day prior, this assessment does not need to be repeated at Cycle 1, Day 1)
- CBC with differential (results to be submitted to central laboratory; if Baseline Visit activities occur within 1 day prior, this assessment does not need to be repeated at Cycle 1, Day 1)
- Pregnancy test for patients of childbearing potential (If Baseline Visit activities occur within 1 day prior, this assessment does not need to be repeated at Cycle 1, Day 1)
- Coagulation parameters (fibrinogen, INR, PT, and aPTT) (results to be submitted to central laboratory; if Baseline Visit activities occur within 1 day prior, this assessment does not need to be repeated at Cycle 1, Day 1)
- Eye exam performed by investigator
- Predose blood sample for PK evaluation (within 24 hours) (Cycles 1, 2, 3, 4, 7, and every 3rd cycle thereafter)
- Predose blood sample for ATA evaluation (within 24 hours) (Cycles 1, 2, 3, 4, 7, and every 3rd cycle thereafter)
- Predose blood sample for plasma proteomic analysis (within 24 hours) (Cycles 1, 2, 3, 4, 7, and every 3rd cycle thereafter)
- Predose blood sample for plasma mutational analysis (within 24 hours) (Cycles 1, 2, 3, 4, 7, and every 3rd cycle thereafter)
- Predose blood sample for plasma exosome analysis (within 24 hours) (Cycles 1, 2, 3, 4, 7, and every 3rd cycle thereafter)
- Predose blood sample for PBMC immune subsets analysis (within 24 hours) (Cycles 1, 2, 3, and 4 only)

- Ocular premedication and preventative eye therapy (see Section 5.4 and Appendix C)
- Ensure patient completes dosing diary
- Parts A and B, US patients only: patient-reported outcomes questionnaires (all questions). If Baseline Visit activities occur within 1 day prior, this assessment does not need to be repeated at Cycle 1, Day 1.
- Tisotumab vedotin administration
- Blood samples for PK evaluation (all time points from end of infusion)
 - End of infusion (+ 15 minutes) (Cycles 1, 2, 3, 4, 7 and every 3rd cycle thereafter)
 - 1 hour (\pm 15 minutes) (Cycle 1 only)

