PK/ATA/ Biomarker Samples	Study drug administration				X	X	X			
Response Assessment	Biopsy collection	X						See schedules in Appendix B and Appendix C		
	Blood/tissue sample collection							X ^{I,N}		
Parts A and B US only: Patient-Reported Outcomes: PROMIS ^M	Imaging	X					Every 6 weeks ^J	X ^K		
Parts A and B US only: Patient-Reported Outcomes: PRO-CTCAE ^M	CA-125 blood collection	X					Every 6 weeks ^L	X ^K		
Subsequent Anti-Cancer Therapy Status	Questionnaires			X	X ^F			X		
Survival Status	Questionnaires			X			To be collected weekly ±2 days, starting on C1D1 and continuing weekly through EOT ^F			

A	Day 1 of cycle 1 is to be performed no more than 28 days after the screening visit. Day 1 of cycle 2 is to be performed 28 days \pm 3 days after Day 1 of cycle 1. Day 1 of cycle 3 is to be performed 28 days \pm 1 days after Day 1 of cycle 2 etc.	I	From time of informed consent.
B	EOT evaluations should be obtained before the initiation of non-protocol therapy. If EOT evaluations are completed before 30 days following the last study treatment, conduct a phone screen 30–37 days following the patient's last study treatment to ensure that no changes in AE profile have occurred.	J	CT or MRI scans must be performed every 6 weeks (\pm 7 days) for 6 months after the first study drug administration (regardless of study drug administration delays) and every 12 weeks (\pm 7 days) for the next 6 months (regardless of study drug administration delays) and every 6 months (\pm 2 weeks) thereafter. Responses must be evaluated with a confirmatory scan at least 4 weeks after initial response. Scans are to be performed until disease progression, start of new anti-cancer therapy, study termination, or death. Time points for radiographic exams should be calendar based and do not depend on cycle visits. CT of chest/abdomen/pelvis.
C	A telephone call should be performed in order to collect information of survival and new anti-cancer treatment as specified in Section 6.7.	K	Not required if conducted within 4 weeks prior to EOT.
D	Height measurement needed at screening visit only.	L	Blood collection for CA-125 should coincide with imaging visits (see timeline in footnote K) as closely as possible (\pm 5 days). Collected locally. Results are to be submitted to the central laboratory.

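### The catch-all DLT bullet in Protocol 3.1.1 carries a redundant first-cycle limit that, read literally, can leave out a late event when Cycle 2 starts early

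*Protocol*

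**What the plan says.** Protocol Section 3.1.1 sets the period: "The DLT evaluation period for each safety run-in patient is defined as 28 days after the first dose of tisotumab vedotin". The lead-in to the list of DLT criteria repeats the 28 days and requires that the event be related to the drug, so both conditions apply to every bullet.

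One bullet adds its own time limit. The catch-all for Grade 3 or higher non-hematological AEs covers those "which occur during the first treatment cycle and are at least possibly study drug related". No other bullet mentions a cycle.

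Three places govern when dose-dense Cycle 2 may begin, and none makes an exception for the run-in:

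- Section 6.4.1 is headed "Day 1 (± 1 day), All Treatment Cycles (Exceptions Noted"), which allows one day early.
- Appendix A, dose-dense footnote A: "Day 1 of cycle 2 is to be performed 28 days" after Day 1 of Cycle 1, with a window of 3 days either side.
- Section 5.2.3: if only the Day 1 dose was given and Days 8 and 15 are skipped, "the patient could resume the next cycle as early as Day 22 (new Day 1"), subject to the mitigation plans in Section 5.3.

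The count feeds a rule that turns on one patient. The Synopsis and Section 3.1 call a dose level safe and tolerable if "no more than 1 patient experiences a DLT among 6 patients during the DLT period". Section 3.2.2 sets out de-escalation "If DLTs are experienced in 2 or more patients at the 0.9 mg/kg dose during the safety run-in". Under Section 9.3.1.7 a treated patient is DLT-evaluable if she completes the evaluation period or has a DLT. Neither document fixes the first treatment cycle at 28 days for DLT purposes or says which limit prevails. The SAP has no DLT definition of its own.

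**The concern.** Because the lead-in already sets 28 days, the cycle phrase does no work when dosing is on schedule. When Cycle 2 starts early, all it can do is narrow the definition. It cannot widen it, because a late Cycle 2 still meets the 28-day cap.

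The catch-all is where a related severe toxicity without its own bullet has to be counted. Grade 3 fatigue is an example; fatigue was the most frequent Grade 3 or higher AE in the earlier trials, at 9% (Section 1.3.3.1). If such an event occurs after an early Cycle 2 start but before Day 28, a literal reader would not call it a DLT. The patient has completed the 28 days, so she is not replaced and stays among the 6 as a patient without a DLT.

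DLT incidence is part of the run-in primary endpoint. If the uncounted patient were the second of 6, the count would read 1 of 6 instead of 2 of 6 and would favour calling the dose safe. Two sites could also classify the same event differently.

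**Working it through.** The plan gives no figure to reproduce here. The check is calendar arithmetic, followed by an illustration on assumed inputs.

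**Days outside the bullet.** Take the first dose as Study Day 1 and the DLT period as Days 1 to 28. Days lost = 28 − (study day of Cycle 2 Day 1 − 1).

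| Cycle 2 Day 1 | Source | Study day | Days lost |
|---|---|---|---|
| On schedule | 4-week cycle | 29 | 28 − 28 = 0 |
| 1 day early | 6.4.1 | 28 | 28 − 27 = 1 |
| 3 days early | Appendix A, footnote A | 26 | 28 − 25 = 3 |
| Earliest restart | 5.2.3 | 22 | 28 − 21 = 7 |

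If the period is read as ending on Day 29, each count rises by 1.

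**Which events are exposed.** Only those that meet the catch-all and nothing else. Ocular events, major bleeding, the listed hematological events, neuropathy, infusion-related events, severe skin reactions and persistent nausea, vomiting or diarrhea have their own bullets without a cycle limit, and are unaffected when they meet them.

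**Illustration of the effect on the 1-of-6 rule.** The documents give no early-start rate and no onset times, so every input below is assumed:

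- p, true chance of a DLT per patient: 0.20 to 0.40
- s, share of DLT patients who rely only on the catch-all: 0.25 to 1
- r, share of patients who start Cycle 2 early: 0.05 to 0.20
- d, days lost: 1, 3 or 7, with onset even over 28 days and independent of early start

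A true DLT patient goes uncounted with probability q = s × r × d/28. Counted DLTs never exceed true DLTs, so

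Pr(true ≥ 2 and counted ≤ 1) = Pr(Bin(6, p(1 − q)) ≤ 1) − Pr(Bin(6, p) ≤ 1).

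Worked case, d = 7, s = 1, r = 0.20: q = 1 × 0.20 × 7/28 = 0.05.

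- p = 0.30: 45.3% − 42.0% = 3.3%
- p = 0.35: 35.3% − 31.9% = 3.4%, about the maximum over this range of p

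| d | Lowest (p = 0.20, s = 0.25, r = 0.05) | Highest (s = 1, r = 0.20, p near 0.33 to 0.35) |
|---|---|---|
| 1 | 0.02% | 0.5% |
| 3 | 0.07% | 1.4% |
| 7 | 0.15% | 3.4% |

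A middle case at d = 7 (p = 0.30, s = 0.5) gives 0.4% at r = 0.05 and 1.6% at r = 0.20. The result is roughly proportional to r.

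**A second view.** Suppose exactly one of the 6 restarts on Day 22 and all DLTs rely on the catch-all. Her chance of a counted DLT is p × 21/28 = 0.75p, and Pr(counted ≤ 1) = (1 − p)^5 + 5p(1 − p)^4 × (1 − 0.75p). At p = 0.25 this is 55.9%, against 53.4% with full coverage. At p = 0.40 it is 25.9% against 23.3%.

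**After the edit.** With the cycle phrase gone, d = 0 in every row and q = 0.

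**The case against.** The strongest reply is that the two limits are meant to be the same. DLTs are assessed only in the run-in, the run-in uses only the dose-dense regimen, and that cycle is 28 days. A sensible reader could take the first treatment cycle as those nominal 28 days, and the gap disappears. That reading is available. It is not the only one, because Section 5.2.3 calls Day 22 the new Day 1 of the next cycle, and no text settles the matter.

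A second reply is that 7 days is a ceiling. It needs both Day 8 and Day 15 to be skipped, and a restart exactly on Day 22. Section 5.2.3 eliminates the Day 15 dose only after a hold of more than 7 days, so a dose on Day 22 may still be the delayed Day 15 dose of Cycle 1. Many severe toxicities that would cause such holds are already DLTs; the rule counts patients, and those patients would normally receive no further drug. This stands. The exposed patient is one held for a toxicity that was not a DLT, who restarts and then has her only qualifying event by Day 28.

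Third, the count does not decide alone. Moving to 1.2 mg/kg is open only "if 0.9 mg/kg is deemed to be safe by the SMC". The safety reviews run 28 days from dosing, not by cycle number (Protocol Section 1.4; SAP Section 8), and the primary endpoint also includes other unacceptable toxicities. The SMC would see the event and could act. This stands too, although it would mean looking past the written definition. The SMC charter is not among the documents, so how the committee would treat such an event is unknown.

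A reader might infer that the plan flatly excludes these events, that a week of the DLT period is routinely lost, or that the wording would push an unsafe dose forward. The documents support none of these: nothing is lost on schedule, a nominal 28-day reading is open, and SMC judgement sits behind the count.

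**Conclusion.** The point holds as a wording defect in a primary-endpoint definition. The catch-all bullet carries a limit that the lead-in makes unnecessary. Under early Cycle 2 starts that the protocol permits, it can be read to leave 1, 3 or at most 7 days of the DLT period uncovered for events that meet only that bullet.

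The probability of a changed decision cannot be computed from the documents. The upper figures of about 0.5%, 1.4% and 3.4% require every DLT patient to rely on this bullet alone, one patient in five to start Cycle 2 early by the full amount, and even onset over 28 days. That first assumption is hard to credit, since the three AESI groups (ocular, neuropathy, bleeding) all have bullets of their own. The figures also precede any SMC judgement. The practical effect is likely small. This is an optional improvement, worth making because it removes an ambiguity at almost no cost.

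**What to change.** In the catch-all bullet of Protocol Section 3.1.1, delete the clause that limits events to the first treatment cycle and let the 28-day lead-in govern. Alternatively, replace that limit with 28 days from the first dose. The relatedness and laboratory-abnormality parts of the bullet stay as they are, and no other section needs to change.

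The cost is one phrase in an amendment, with no new data, visits or scheduling limits. No protection is lost, because the lead-in already caps every DLT at 28 days.

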3.2 Discussion and Rationale for Study Design

Therapies available to patients with PROC that have previously received 1 to 3 prior lines therapy, including bevacizumab, have poor response rates of around 12% in the first line setting and their effectiveness declines further in the second line and beyond. Long-term survival of patients with PROC is very low.

Patients with ovarian cancer have significant unmet medical need for therapies that can provide meaningful improvement. Tisotumab vedotin has been examined in a limited number

of patients with ovarian cancer in the GEN701 and GEN702 trials. These initial data show activity and need to be explored further in this population with high unmet need. Limited available data indicate that the dose-dense regimen may yield improved efficacy with the same or somewhat higher dose intensity as the Q3W regimen. Previously, dose-dense regimens, including 0.9 mg/kg and 1.2 mg/kg 3QW4, were tested in GEN702 patients without a comprehensive ocular mitigation plan, or strict dose modification guidelines for ocular toxicities in place. With appropriate ocular mitigation steps and dose-reduction guidelines, the dose dense schedule may be both tolerable and efficacious for this patient population.

3.2.1 Method of Assigning Patients to Treatment Groups

In the safety run-in portion of the study, each dose level will enroll sequentially starting at 0.9 mg/kg using the dose-dense schedule.

Part A will begin enrollment after the safety run-in period is completed. Patients will be randomly assigned to 1 of 2 dosing schedules in a 1:1 ratio. Randomization is intended to avoid bias and minimize imbalance between 2 dosing schedules on key prognostic factors for the purpose of evaluating safety and activity of the dose-dense and Q3W schedules.

Randomization will be centrally controlled and stratified by first line vs. second line PROC and histology (serous vs. non-serous). At the time of randomization, a unique randomization number will be assigned to identify the dose regimen (dose-dense or Q3W) the patient is allocated to. Randomization procedures are detailed in the Study Manual.

Part B will have a single treatment arm and will begin enrollment of patients after 0.9 mg/kg dose-dense is deemed safe and tolerable in the safety run-in, if this occurs.

